8.1 Event Terminology

Adverse Event: Any untoward medical occurrence associated with the use of a drug in humans, whether or not considered drug related.

Serious Adverse Event: An adverse event is considered “serious” if, in the view of either the investigator or sponsor, it results in any of the following outcomes:

- Death
- A life-threatening adverse experience
- Inpatient hospitalization or prolongation of existing hospitalization
- A persistent or significant incapacity or substantial disruption of the ability to conduct normal life functions
- A congenital anomaly/birth defect
- Important medical events that may not result in death, be life-threatening, or require hospitalization may be considered serious when, based upon appropriate medical judgment, they may jeopardize the patient or subject and may require medical or surgical intervention to prevent one of the outcomes listed in this definition.

Unexpected Event: An adverse event or suspected adverse reaction is considered “unexpected” if it is not listed in protocol-related documents (e.g. protocol, consent documents), or is not listed at the specificity or severity that has been observed or given the characteristics of the subject population being studied.

The following definitions are from the Masonic Cancer Center’s Data and Safety Monitoring Plan (<http://z.umn.edu/dmsp>)

Major Deviation: A deviation or violation that impacts the risks and benefits of the research; may impact subject safety, affect the integrity of research data and/or affect a subject’s willingness to participate in the research. Deviations that place a subject at risk, but do not result in harm are considered to be major deviations.

Minor Deviation: A deviation or violation that does not impact subject safety, compromise the integrity of research data and/or affect a subject’s willingness to participate in the research.

8.2 Event Monitoring and Documentation

This study involves collecting samples for research related purposes in patient undergoing standard of care RE therapy. Event monitoring will focus on risks associated with study procedures, including sample collection (blood and tumor) and breach of confidentiality. However, all AEs will be documented and reported as required.

8.3 Expedited Reporting Requirements

The following situations must be reported to the UMN IRB in an expedited manner:

Agency reporting to	Criteria for reporting	Timeframe	Form to Use	Submission address/email address
U of MN IRB	Unanticipated death of a locally enrolled subject(s); New or increased risk; Any adverse event that require a change to the protocol or consent form – refer to the IRB website for complete details	5 Business Days	IRB Report Form	[contact]
	Major Deviations that occur at MCC, as defined in Section 10.1.	5 Business Days	OnCore Deviation Form and IRB Report Form	

9 Study Data Collection and Monitoring

9.1 Data Management

Participants will be registered in OnCore as detailed in Section 4.1. Study data will be collected in REDCap.

9.2 Data and Safety Monitoring Plan (DSMP)

The study's Data and Safety Monitoring Plan will be in compliance with the University of Minnesota Masonic Cancer Center's Data & Safety Monitoring Plan (DSMP), which can be accessed at <http://z.umn.edu/dsmp>

For the purposes of data and safety monitoring, this study is classified as high risk (investigator initiated). Therefore, the following requirements will be fulfilled:

- The Masonic Cancer Center Data and Safety Monitoring Council (DSMC) will review the study's progress at least quarterly.
- The PI will comply with at least twice yearly monitoring of the project by the Masonic Cancer Center monitoring services.
- The PI will oversee the submission of all reportable adverse events per the definition of reportable in Section 10.3 to the Masonic Cancer Center's SAE Coordinator and the University of Minnesota IRB.

9.3 Monitoring

The investigator will permit study-related monitoring, audits, and inspections by the Masonic Cancer Center or their designee, IRB, government regulatory bodies, and University of Minnesota compliance groups. All study related documents (e.g. source documents, regulatory documents, data collection instruments, study data, etc.) will be made available. The investigator will ensure the capability for inspections of applicable study-related facilities (e.g. pharmacy, diagnostic laboratory, etc.) will be available for trial related monitoring, audits, or regulatory inspections.

9.4 Record Retention

The investigator will retain study records including source data, copies of case report form, consent forms, HIPAA authorizations, and all study correspondence in a secured facility for at least 6 years after the study file is closed with the IRB.

10 Statistical Considerations

Descriptive statistics will be calculated for outcomes and variables of interest. Continuous variables will be summarized using mean and standard deviation, or median and interquartile range, as appropriate. Categorical variables will be summarized using frequencies and percentages. Plots of each peripheral lymphocyte at baseline and each subsequent time of measurement (as stated in the protocol synopsis section) will be generated. This will help determine if individuals have different baseline peripheral lymphocyte values or different peripheral lymphocyte value trends over time. Similar plots will be generated for each cytokine (*IL-1 α* , *IL-1 β* , *IL-2*, *IL-6*, *IL-10*, *IL-12p70*, *IL-18*, *TNF α* , *IFN-Y*, *Fit ligand 3*, and *MCP-1*).

Primary analysis: To determine if there is a change in peripheral lymphocytes following RE, a mixed model with random intercept and random slope for time, and adjustment for baseline peripheral lymphocyte value will be carried out for each lymphocyte. The fixed effect for time, representing the slope over time, will be tested for significance, and a 95% confidence interval will be reported. Depending on if the outcome is skewed, appropriate transformations will be used. Similar models may be carried out with adjustment for certain variables such as age, sex, and size of tumor. Additionally, to investigate specific changes in peripheral lymphocytes from baseline, pairwise comparisons between baseline and each measurement following RE, using paired t-tests or Wilcoxon signed-rank tests, will be performed with a Bonferroni adjustment for multiple comparisons.

Secondary analysis: To determine if there is a change in active cell infiltration into tumors following RE, paired t-tests or nonparametric Wilcoxon signed-rank tests will be used, depending on the distribution of the outcome. These analyses will be performed for the different tumor types (treated and non-treated tumors). In the case that certain variables such as age, sex and size of tumor are of interest, a mixed model will be obtained using an appropriate distribution assumption of the outcome (e.g. Gaussian, Poisson or negative binomial).

To determine if there is a change in cytokine production following RE, an analysis similar to the primary analysis will be performed for each cytokine.

Statistical analyses will be performed using SAS 9.4 (SAS Institute Inc., Cary, NC) or R 3.4.2. All p-values reported will be two-sided and a significance level of 0.05 will be used.

11 Ethical and Regulatory Considerations

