IRB	Institutional Review Board
PBMC	peripheral blood mononuclear cell
RE	Radioembolization
UMN	University of Minnesota
Y90	Yttrium 90
XRT	External beam radiation

Protocol Synopsis

Radioembolization of Primary and Secondary Liver Malignancies and the Effect On the Immune System

CPRC #2018LS026

Study Design: This is a single institution non-interventional study designed to evaluate the immune reaction to radioembolization (RE) of primary and secondary malignancies of the liver.

RE has been established as a standard of care treatment for both primary and secondary cancers of the liver. The treatment consists of a mapping, or planning angiogram, followed by a delivery angiogram where the dose of yttrium 90 (y90) is delivered. Data has been published on the immune modification powers of external beam radiation (XRT). However, very little data is available on the ways in which RE modifies the immune system. The goal of this study is to determine changes in the peripheral blood monocytes, cytokines and the treated and untreated liver tumors through sample collection prior to and for 12 weeks after standard of care RE.

Prior to the RE delivery procedure, patients will have a blood draw to evaluate for levels of 11 immunologically relevant cytokines (IL-1 α , IL-1 β , IL-2, IL-6, IL-10, IL-12p70, IL-18, TNF α , IFN- γ , Fit ligand 3, and MCP-1). These blood draws will be repeated at 7 days (\pm 6 days), 4 weeks (\pm 2 weeks) and 12 weeks (\pm 2 weeks) after RE.

The patients will also have the infiltration of immune relative cells into treated tumors evaluated. This will be done by the patients undergoing biopsy of the largest tumor to be treated prior to treatment and optionally at 2 weeks (\pm 7 days) following RE. If patients have other areas of tumor, which are not included in the initial treatment site, these areas will also be biopsied.

Finally, the change in immunologically important peripheral lymphocytes will be collected. This will be done with a blood draw on the day of, but prior to RE serving as an internal control. Patients will then also have blood draws performed at 7 days (\pm 6 days), 4 weeks (\pm 2 weeks) and 12 weeks (\pm 2 weeks) after RE.

Primary Objective: Determine changes in the peripheral blood lymphocytes after radioembolization (RE) therapy for primary and secondary malignancies of the liver at 12 weeks.

Secondary Objectives:

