Clinical follow up with magnetic resonance imaging (MRI) or CT will occur at 1 month and 3 months. Radiologic response will be evaluated at 3 months using Response Evaluation Criteria in Solid Tumors (RECIST) and modified RECIST guidelines. Overall survival will be defined as time from RE to death, and patients will be censored for transplantation. Progression free survival will be defined as time from RE to progression as defined by RECIST and mRECIST.

Peripheral blood monocytes will be collected and processed for flow cytometric analyses and cryostorage for later batch studies. The effect RE on lymphocyte repertoire, numbers and phenotype will be assessed at baseline and at defined time points during the trial (7 days (+/- 6 days), 4 weeks (+/- 2 weeks), and 12 weeks (+/- 2 weeks). The frequency and percentage of peripheral blood monocytes and T-cell subsets (CD4 and CD8 effector memory, central memory and Treg subsets), NK cells and myeloid-derived suppressor cells will be determined. Peripheral blood tumor-specific T cell subsets will be evaluated by flow cytometry in cooperation with the Translational Therapy Laboratory, Masonic Cancer Center. Cytotoxic T lymphocytes (CD8+ T cells) and CD4+ helper T cells will be isolated using fluorescence-activated cell sorting (FACS) from cryopreserved cells followed by mRNA expression analysis to assess gene expression changes resulting from therapy. Testing will be performed in the UMN Flow Cytometry and Genomics Core Laboratories. Peripheral blood monocytes may also be tested in functional assays (i.e. IFN- γ ELISpot) for responses to known antigens as well as to predicted neoantigens from whole-exome/transcriptome sequencing of melanoma tumors. All patients will also undergo HLA testing to enable epitope discovery using available MHC binding prediction algorithms.

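### The primary mixed model tests a single slope over time adjusted for baseline, which is not the change from before RE to week 12, and the plan does not say whether this slope or the planned paired test decides the 12-week objective

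*Combined protocol and SAP*

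**What the plan says.** The primary objective in the Protocol Synopsis is: "Determine changes in the peripheral blood lymphocytes after radioembolization (RE) therapy for primary and secondary malignancies of the liver at 12 weeks". The Synopsis describes the lymphocyte sample taken before treatment as the reference: "This will be done with a blood draw on the day of, but prior to RE serving as an internal control". Section 7.3 also places the primary endpoint at 12 weeks. Blood is drawn before RE and at nominal weeks 1, 4 and 12. There is one cohort, with an accrual goal of 30.

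Section 10, Primary analysis, gives its purpose as "To determine if there is a change in peripheral lymphocytes following RE". It specifies a mixed model in which each patient has their own intercept and time slope as random effects. On baseline it says: "and adjustment for baseline peripheral lymphocyte value will be carried out for each lymphocyte". It then names the tested parameter: "The fixed effect for time, representing the slope over time, will be tested for significance". The text does not say which visits form the response.

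Later in the same paragraph, introduced as an addition, come "pairwise comparisons between baseline and each measurement following RE", by paired t-test or Wilcoxon signed-rank test with a Bonferroni adjustment. For cytokines, "an analysis similar to the primary analysis will be performed for each cytokine".

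**The concern.** In a study with no comparison arm, the sample taken before RE is the only reference for change. Using it as a covariate ordinarily takes it out of the response, which leaves weeks 1, 4 and 12. The time effect is then movement between visits that all follow treatment. Any shift between the RE-day draw and the first later draw is absorbed by the intercept and the baseline coefficient, and neither of these is tested. Making visit categorical would not help while baseline stays only a covariate to the raw values, because the visit contrasts would still compare one later visit with another.

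An early fall that persists could therefore give a null slope, and an early fall that partly recovers could give a significantly positive one, while week 12 is still below baseline. The plan has no rule for a slope and a week-12 paired test that disagree. The 11 cytokine analyses take over the same model.

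**Working it through.** **Inputs.** From the documents: visits at nominal weeks 0 (RE day), 1, 4 and 12; n = 30; two-sided 0.05. The documents give no effect size, SD, correlation or power, so there is no planned figure to reproduce. Assumed: log scale; two mean courses at weeks 1, 4 and 12 relative to baseline, A (-0.30, -0.30, -0.30) and B (-0.50, -0.40, -0.30); residual SD σ from 0.20 to 0.35; random-slope SD 0.01 per week; complete data at nominal times. Both courses end at -0.30, and exp(-0.30) = 0.74, which is 26% below baseline.

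**Formula.** The expected slope is Σ(t - t̄)y / Σ(t - t̄)². With complete balanced data, a covariate that is constant within patient does not change the estimated slope, so least squares on the mean course gives the model's expected slope.

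**Reading 1: baseline is a covariate only (weeks 1, 4, 12).** t̄ = 5.667; deviations -4.667, -1.667, 6.333; Σ(t - t̄)² = 64.67.
- A: the course is flat, so the slope is 0.
- B: (2.333 + 0.667 - 1.900)/64.67 = 1.100/64.67 = +0.0170 per week, or +0.20 over 12 weeks.

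**Reading 2: baseline is a covariate and also a response (weeks 0, 1, 4, 12).** t̄ = 4.25; deviations -4.25, -3.25, -0.25, 7.75; Σ(t - t̄)² = 88.75; the mean at week 0 is 0.
- A: (0.975 + 0.075 - 2.325)/88.75 = -1.275/88.75 = -0.0144 per week, or -0.17 over 12 weeks.
- B: (1.625 + 0.100 - 2.325)/88.75 = -0.600/88.75 = -0.0068 per week, or -0.08 over 12 weeks.

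The true 12-week change is -0.30 in all four cases. In Reading 2 the covariate equals the response at week 0, so it adds nothing to the slope and conflicts with constant residual variance.

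**Rejection rates.** The SE of the slope is √{(σ²/Σ(t - t̄)² + 0.01²)/30}. The SE of the week-12 minus baseline difference is √{(2σ² + (12 × 0.01)²)/30}. Power is from the noncentral t distribution with 29 df; ranges run from σ = 0.35 to σ = 0.20.

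| Test | Course A | Course B |
|---|---|---|
| Slope, Reading 1 | 5% (the type I error rate) | significantly positive in 52% to 92% |
| Slope, Reading 2 | significantly negative in 51% to 90% | significantly positive in under 1% |
| Week 12 vs baseline, 0.05 | 88% to >99% | 88% to >99% |
| Week 12 vs baseline, 0.05/3 | 75% to >99% | 75% to >99% |

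For example, the slope in Reading 1, course B, σ = 0.35 has SE = √{(0.1225/64.67 + 0.0001)/30} = 0.00815, so 0.0170/0.00815 = 2.09 and power is 52%. The week-12 difference at σ = 0.35 has SE = √{(0.245 + 0.0144)/30} = 0.0930, so 0.30/0.0930 = 3.23 and power is 88%. The divisor 3 assumes a Bonferroni family of three visits within one lymphocyte; the plan does not define the family.

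**The case against.** The strongest reply is that the plan already contains the right comparison. The paired tests stand in the Primary analysis paragraph itself, they compare each visit with baseline, and under the assumptions above the week-12 test has 75% to >99% power even at 0.05/3. The cytokine analysis plausibly inherits them. A reader might infer that the study has no valid test of change from before RE, or would report only a null or a reversed result. The documents do not support that. What remains is that the paired tests are introduced as additional to a model whose slope is the parameter named for testing, and nothing ranks the two.

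A second reply is that the text never removes the baseline row from the response. The plots planned just before it run from baseline onward and are meant to show differing baselines and trends, which fits a random intercept at time zero. This also stands: removal is an inference from ordinary usage. It matters for size, because the sign reversal for course B occurs only under Reading 1. A steeper assumed recovery (-1.0, -0.7, -0.3 in SD units) does give a positive slope under Reading 2, (3.25 + 0.175 - 2.325)/88.75 × 12 = +0.15, but reversal is not a general result there. Neither reading makes the slope equal to the 12-week change for these courses. A steady linear change starting at RE would be recovered.

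Finally, this is a 30-patient, non-interventional, single-institution study. That lowers the stakes, but the section still names a primary analysis tested at 0.05.

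**Conclusion.** The point holds as a mismatch between objective and tested parameter, together with an unstated hierarchy. For an abrupt change, the slope is 0 or of the wrong sign under the usual reading of baseline adjustment. If baseline is also kept as a response, the slope recovers -0.17 or -0.08 of a true -0.30. These slopes follow from the nominal visit times and the assumed mean courses, not from any SD; the rejection rates also depend on the assumed SDs. It would go too far to call the primary analysis invalid as a whole, since the paired tests give a valid comparison with baseline. It would also go too far to say the model certainly excludes the baseline row, since the plan is silent on this. The severity is should-fix: the analyst needs to be told which model is meant and which result answers the 12-week question.

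**What to change.** Delete the baseline covariate from the primary model. Enter the RE-day value as the response at time zero, treat visit as categorical, and name the week-12 minus baseline contrast as the primary test, with 7 days and 4 weeks secondary. Categorical visit is essential: with linear time, a contrast against time zero is only the slope multiplied by weeks, so deleting the covariate alone would still give -0.17 and -0.08.

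If the covariate is wanted, an alternative is to model change from baseline by categorical visit, centre baseline at its mean, and test the adjusted mean change at week 12 against zero.

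In either case, keep the slope as descriptive, state how the paired tests relate to the primary contrast, and apply the same wording to the cytokines. The cost is SAP wording only; no new samples or visits are needed.

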7.2 Research Related Sample Collection

	Prior to RE	Time post RE			
		1 week (± 6 days)	2 weeks (±7 days) optional	4 weeks (± 2 weeks)	12 weeks (± 2 weeks)
Assess for adverse events		X	X	X	X
Peripheral blood for cytokines	X	X		X	X
Peripheral blood for lymphocytes	X	X		X	X
Tumor biopsy	X		X a treated and an untreated tumor		

Research sample collection will be tied to the clinical care time points whenever possible. It is recognized that with novel therapies as used in this study, the timing of protocol directed research samples may miss important patient specific events. For this reason, up to 3 extra samples for a total of 180 ml of blood may be drawn at additional time points that are not specified above. This blood would be drawn in the case that blood draws from specified time points were damaged, lost, or unusable.

7.3 Endpoints, detailed:

The primary endpoint for this study is to determine changes in the peripheral blood monocytes after RE therapy for primary and secondary malignancies of the liver at 12 weeks.

Secondary endpoints include the changes in peripheral blood monocytes at 7 days and 4 weeks. The changes in immunologically relevant cytokines (*IL-1 α , IL-1 β , IL-2, IL-6, IL-10, IL-12p70, IL-18, TNF α , IFN- γ , Fit ligand 3, and MCP-1*) at 7 days, 4 weeks, and 12 weeks will also be determined. Biopsies of the treated tumor prior to treatment and 2 weeks after treatment (if done) will also be performed to assess immune cell infiltration following treatment. The 2-week after treatment biopsy will be performed strictly for research purposes and will be optional. The second biopsy was made optional as it was found to be a significant barrier to enrollment. Furthermore, the change in PBMCs is the most scientifically important aspect of the study. Additionally, when available, a non-treated tumor will be biopsied two weeks after treatment to assess for immune cell infiltration.

7.4 Research data collection and lab analyses detailed:

Basic characteristics of the malignancy (type of malignancy, size of largest tumor, and number of tumors) will be recorded. RE will be completed in a manner which has been previously described (20). All of the preprocedural work up and procedure costs will be billed to insurance as this is standard of care.

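### The primary test and 95% CI go to a linear slope, while the stated primary target is the 12-week change from baseline

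*Combined protocol and SAP*

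**What the plan says.** The synopsis states the primary objective as "Determine changes in the peripheral blood lymphocytes after radioembolization (RE) therapy for primary and secondary malignancies of the liver at 12 weeks" and treats the blood draw just before radioembolization (RE) as each patient's internal control. Section 7.3 gives the primary endpoint the same time point: "determine changes in the peripheral blood monocytes after RE therapy for primary and secondary malignancies of the liver at 12 weeks". (It names monocytes where the synopsis names lymphocytes; that mismatch is a separate matter.) Section 7.3 then places the earlier visits lower: "Secondary endpoints include the changes in peripheral blood monocytes at 7 days and 4 weeks". Section 1.1 repeats the primary objective without a time point.

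Section 10, under its primary analysis, specifies "a mixed model with random intercept and random slope for time, and adjustment for baseline peripheral lymphocyte value will be carried out for each lymphocyte". Inference is attached to one coefficient: "The fixed effect for time, representing the slope over time, will be tested for significance, and a 95% confidence interval will be reported". The comparisons with baseline come afterwards: "Additionally, to investigate specific changes in peripheral lymphocytes from baseline, pairwise comparisons between baseline and each measurement following RE", by paired t or Wilcoxon signed-rank tests with a Bonferroni adjustment. Week 12 is not singled out among them. For cytokines, "an analysis similar to the primary analysis will be performed for each cytokine".

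**The concern.** The slope answers how fast the marker changes per week along a straight line. The primary objective asks how far the marker is from its pre-treatment value at 12 weeks. The two are certain to agree only when the mean course is linear, and nothing in the documents argues that it is.

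Section 10 also leaves open whether the pre-RE value is only a covariate or is also a row of the outcome. If it is only a covariate, the slope is estimated from weeks 1, 4 and 12 and describes drift among post-treatment visits, with no comparison with baseline in it. If it is also an outcome row, a line through weeks 0, 1, 4 and 12 can still misstate the week-12 change.

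The primary analysis therefore holds two tests of different questions and no rule for which one answers the objective. If they disagree, the choice would be made after seeing the data. The paired week-12 test is the one that matches the objective, but it has no CI and pays a Bonferroni penalty for the 7-day and 4-week comparisons that section 7.3 calls secondary.

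**Working it through.** The documents give no power statement, effect size or SD, so there is no planned figure to reproduce. The check is on what the slope estimates.

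**Inputs from the documents.** Draws before RE and at 7 days (±6 days), 4 weeks (±2 weeks) and 12 weeks (±2 weeks) (section 7.2); 30 patients (synopsis); two-sided 0.05 (section 10).

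**Slope weights.** With equal weight per visit, slope = Σ(t − t̄)y / Σ(t − t̄)².
- Baseline as covariate only (weeks 1, 4, 12): t̄ = 5.667, Σ(t − t̄)² = 64.67, weights −0.0722, −0.0258, 0.0979.
- Baseline also an outcome row (weeks 0, 1, 4, 12): t̄ = 4.25, Σ(t − t̄)² = 88.75, weights −0.0479, −0.0366, −0.0028, 0.0873.

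**Slope × 12 against the true 12-week change.** These results need no variance assumption.

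| Mean change at weeks 1, 4, 12 | True 12-week change | Covariate only | Outcome row |
|---|---|---|---|
| Lasting step: −1, −1, −1 | −1 | 0 | −0.575 |
| Dip, recovered: −1, −0.5, 0 | 0 | +1.02 | +0.46 |
| Dip, half recovered: −1, −0.75, −0.5 | −0.5 | +0.51 | −0.06 |

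For example, the step with the outcome row gives 12 × (0.0366 + 0.0028 − 0.0873) = −0.575. The recovered dip with covariate only gives 12 × (0.0722 + 0.5 × 0.0258) = +1.02.

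Within the draw windows, the 57% for the step ranges from 36% (weeks 1 and 4 early, week 12 late) to 90% (the reverse). These extremes need opposite edges at different visits. If all draws are early it is 54%, and if all are late 57%.

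**Rejection rates.** Assumed: n = 30, complete data, normal outcomes, SD 1 before random slopes, correlation 0.5 to 0.7, nominal visit weeks, and one-sample t tests on per-patient slopes or differences. The Bonferroni level is 0.05/3 = 0.0167.

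| Scenario | Slope, covariate only | Slope, outcome row | Week-12 paired, Bonferroni | Week-12 paired, 0.05 |
|---|---|---|---|---|
| Step 0.6 SD, no random slope | 5% | 53–74% | 77–95% | 89–98% |
| Step 0.6 SD, random-slope SD 1 per 12 weeks | 5% | 27–33% | 43–54% | 62–72% |
| Recovered dip 0.8/0.4/0 SD, random-slope SD 0–1 | 84% to >99% | 30–79% | <2% | about 5% |
| Recovered dip 0.4/0.2/0 SD, random-slope SD 0–1 | 32–75% | 11–28% | <2% | about 5% |

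In the dip rows every slope figure is a significant positive slope, although the 12-week change is zero. For the step without random slopes, the slope is non-significant while the Bonferroni week-12 test is significant in 73–91% (covariate only) or 21–25% (outcome row) of trials. With random-slope SD 1 these fall to 40–51% and 16–21%.

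**Fitted mixed model.** A random-intercept, random-slope model with the baseline covariate (correlation 0.6, random-slope SD 0.5, 120 fits per scenario, some with convergence warnings) agrees.
- Step, true change −0.60: mean fitted 12-week change −0.01 (5% rejected) without the baseline row and −0.35 (42%) with it.
- 0.8 SD dip, true change 0: +0.83 (100% rejected) and +0.38 (50%).

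**The case against.** The strongest reply is that the plan already contains the right test. The paired comparisons sit in the same primary-analysis paragraph, and in both scenarios above they behave well: the week-12 test seldom rejects after a recovered dip, and the week-1 test detects the 0.8 SD fall in 96% or more of trials. That is true, and the plan is not blind to the 12-week change. It still leaves those tests without precedence or a CI, and gives the reported interval to the other quantity.

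Second, the 12-week target is not perfectly settled. Section 1.1 has no time point, and the synopsis also lists 12 weeks among the secondary lymphocyte time points. This adds to the ambiguity; it does not make the slope the endpoint.

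Third, the time courses are chosen illustrations, and the starkest figures need the covariate-only reading. With the outcome row, only a week-1 departure from the line matters much: one unit there moves slope × 12 by 12 × 0.0366 = 0.44, against 12 × 0.0028 = 0.03 at week 4. This stands as a limit on size. An early response is nevertheless what the 7-day draw is placed to catch.

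Fourth, this is a small non-interventional study with planned plots, and continuous time suits wide windows. That is a fair reason to keep the slope as supportive. The protocol still names a primary endpoint, a primary analysis and a 0.05 level.

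**Conclusion.** The concern holds and should be fixed. The mismatch between the 12-week target and the tested slope follows from the text, and the slope × 12 results depend only on the visit times and the assumed shape of the course. For a lasting step the slope shows none or 57% of the true change; for a recovered dip it shows a rise when the 12-week change is zero. The rejection rates rest on assumed effect sizes, SDs, correlations and complete data, and show direction and rough size rather than forecasts. If the course is close to linear, the slope and the 12-week change agree and little is lost.

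**What to change.** In section 10:

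- Name the week-12-minus-baseline contrast, with its 95% CI, as the primary test for each lymphocyte, at two-sided 0.05 with no adjustment for the other visits.
- Take it from a mixed model with visit as a four-level factor (pre-RE, 7 days, 4 weeks, 12 weeks), with the pre-RE value as an outcome row and not also as a covariate. State the covariance structure.
- Take the 7-day and 4-week contrasts from the same model as secondary, Bonferroni-adjusted between them (0.05/2 = 0.025 each). Keep the signed-rank test as a check for skewed markers.
- Keep the linear slope, fitted on actual draw dates, as supportive.
- Carry the same structure over to the cytokines.

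In section 1.1, add the 12-week time point. In the synopsis, remove week 12 from the secondary lymphocyte time points.

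The change is wording only and needs no new patients, draws or assays. It has two costs. If the course is exactly linear, with 0.6 SD at week 12, correlation 0.5 and no random slope, power falls from 94% (slope with the baseline row) to 89%. Categorical visits also ignore variation in draw dates inside the wide windows, which the supportive slope partly covers.

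### Holm's step-down adjustment would be a near-free refinement of the valid Bonferroni rule for the baseline-to-visit comparisons

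*Combined protocol and SAP*

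**What the plan says.** Section 10, primary analysis, fits a mixed model for each lymphocyte. Its main test is the slope: "The fixed effect for time, representing the slope over time, will be tested for significance, and a 95% confidence interval will be reported". No multiplicity adjustment is stated for that test.

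The paired tests follow as an addition: "Additionally, to investigate specific changes in peripheral lymphocytes from baseline", the plan makes "pairwise comparisons between baseline and each measurement following RE". The method and the adjustment for these tests are given in one clause: "using paired t-tests or Wilcoxon signed-rank tests, will be performed with a Bonferroni adjustment for multiple comparisons". Section 7.4 sets the post-RE blood draws at "7 days (+/- 6 days), 4 weeks (+/- 2 weeks), and 12 weeks (+/- 2 weeks"), so each marker has three such comparisons.

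For cytokines, Section 10 says that "an analysis similar to the primary analysis will be performed for each cytokine"; the synopsis speaks of "levels of 11 immunologically relevant cytokines". Bonferroni is therefore implied for cytokines but not restated. The overall level is given once: "All p-values reported will be two-sided and a significance level of 0.05 will be used".

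The plan does not say whether the Bonferroni family is the three visits of one marker or also runs across markers. It gives no effect size, SD, target power or dropout rate. The accrual goal is 30 patients.

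**The concern.** Bonferroni holds every comparison to the strictest threshold, even after another visit has already been shown to change. Holm relaxes the threshold step by step at the same family-wise error. In a study of 30 patients, power left unused is worth a second look.

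The paired tests are supplementary, but they are the only stated tests of change from baseline at a named visit, including the 12-week visit on which the primary endpoint rests. At stake is how often a second or third truly changed visit is reported as not significant.

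**Working it through.** **Inputs from the plan.** Two-sided 0.05; three post-RE visits; paired tests; accrual goal 30. There is no power figure in the plan to reproduce.

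**Assumed, because the plan is silent.** Family of three visits per marker; normally distributed changes; standardised change 0.5; correlation 0.5 between changes (they share one baseline); 30 evaluable patients. Ranges are given below.

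**Thresholds.** Bonferroni tests every comparison at 0.05/3 = 0.0167. Holm orders the p-values and tests them at 0.05/3 = 0.0167, 0.05/2 = 0.025 and 0.05/1 = 0.05, stopping at the first failure.

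**Validity.**
- Bonferroni: the thresholds sum to 3 × 0.0167 = 0.05. Under independence the family-wise error is 1 − (1 − 0.0167)³ = 0.0492, against 1 − 0.95³ = 0.1426 with no adjustment.
- Holm: suppose k of the three nulls are true. The first true null to be rejected is met while at least k hypotheses remain, so its p-value is at most 0.05/k. By the union bound the chance of this is at most k × 0.05/k = 0.05, whatever the dependence.
- Every Holm threshold is at least 0.0167, so Holm rejects whatever Bonferroni rejects. The smallest p-value meets 0.0167 under both, so the two always agree on whether any visit is declared changed.

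**Limits on the gain at one visit.** The noncentrality is 0.5 × √30 = 2.739 on 29 degrees of freedom. Exact two-sided paired t-test power is 58.3% at 0.0167 and 75.4% at 0.05. Bonferroni sits at the lower figure; Holm lies between the two.

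**Simulation** (40,000 replicates per setting; the simulated Bonferroni figure per visit came out at 58% to 59%, in line with the exact 58.3%). Each cell shows Bonferroni → Holm:

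| Visits truly changed by 0.5 SD | Power per changed visit | All changed visits shown | At least one visit declared |
|---|---|---|---|
| One | 58% → 58% | 58% → 58% | 60% for both |
| Two | 58% → 62% | 42% → 48% | 75% for both |
| Three | 58% → 67% | 33% → 52% | 83% for both |

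**Sensitivity.**
- Three visits changed, correlation 0 to 0.8: Holm gives 66% to 68% per visit. All three are shown in 20% → 40% (correlation 0) and 42% → 59% (correlation 0.8).
- Three visits changed, 20 evaluable patients: 37% → 44% per visit.
- Unequal changes of 0.8, 0.5 and 0.3 SD: the smallest goes from 20% to 33%.
- No true change: family-wise error is the same for both, about 4.7%.

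**What Holm gives up.** With two visits changed and one null, the false-positive rate at the null visit is 0.05/3 = 1.7% under Bonferroni. Under Holm it is about 3.5% when the real changes are 0.5 SD and between 4.6% and 4.8% when they are 0.8 SD. It stays within 5%.

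**If the family also spans markers.** For 11 cytokines × 3 visits = 33 comparisons, 0.5 SD and 30 patients, power per real change is about 25% under Bonferroni. Holm adds about 1 point if 3 cytokines change, 2 points if 6 change and 4 points if all 11 change. At 0.6 SD with every comparison real, the gain is larger, about 43% to 55%.

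**The case against.** The strongest reply is that nothing here is wrong. Bonferroni is standard, pre-specified and controls the error rate that the plan asks for. No power target is stated that it could cause the study to miss. The affected tests are introduced as additional, and the slope test, which carries the main question, is not Bonferroni-adjusted and would not change. All of this stands, and it is why the point is optional.

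Two stronger readings are tempting, and the documents do not support either:
- A reader might infer that real lymphocyte and cytokine changes will be missed because of Bonferroni. Detection of at least one changed visit never differs, the gain is close to nil if a single visit changes, and the large gains need all three visits to change. The plan gives no effect sizes from which to judge how likely that is.
- A reader might infer that Bonferroni buys nothing. It gives a lower false-positive rate at a null visit when others change, and simple matching simultaneous intervals. Section 10 promises an interval only for the slope, so the second benefit has little weight here, although the plan does not rule such intervals out.

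The family is also undefined. Holm never rejects less than Bonferroni under any family, so its ranking does not depend on this, but the size of the gain does. Nor would Holm settle the family: if each of 11 cytokines is adjusted only across its own visits, the chance of at least one false positive across independent cytokines could reach 1 − 0.95¹¹ = 0.43 under either method.

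Finally, Section 7.3 says that the second biopsy was made optional because it hindered enrollment. That suggests recruitment had begun, so the change may need an amendment with a reason rather than a simple edit.

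**Conclusion.** The point holds as an optional improvement. Bonferroni is valid; Holm gives the same family-wise guarantee and never rejects less. With three visits per marker, 30 patients, 0.5 SD changes and correlation 0.5, the gain per truly changed visit is about 0, 3 to 4, or 9 percentage points as one, two or three visits change. The largest effect is on showing all three changes (33% to 52%). That Holm never rejects less rests on no assumption; the percentages rest on the assumed effect size, correlation, number of evaluable patients and family. The price is a higher false-positive rate at a null visit, within 5%, and the loss of simple matching intervals that the plan does not promise for these tests.

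**What to change.** In the primary-analysis paragraph of Section 10, name Holm's step-down adjustment in place of Bonferroni for the paired comparisons, and keep the family as intended. Add to the cytokine sentence that the same adjustment applies there. State that Holm-adjusted p-values will be reported.

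The cost is a few words and one option in SAS or R, both already named in the plan; no visit, sample or patient is affected. If the protocol is already in force, it should go in as a short amendment made before results are seen. If the sponsor wants simultaneous intervals for the visit changes, keeping Bonferroni is a reasonable choice and needs no defence.
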